8.2.6. Prior and Concomitant Medications and Surgeries/Procedures

Prior and concomitant medications will be coded using World Health Organization Drug Dictionary (WHO DD) version 202203 B3. Prior and concomitant surgeries and procedures will be coded using the Medical Dictionary for Regulatory Activities (MedDRA) version 25.0.

Prior and concomitant medications

SAP

Prior medications include non-study medications that started and ended prior to the first dose of study medication. Concomitant medications include non-study medications with start date on or after the date of the first dose of study medication and no later than 30 days after the last dose of study medication. Medications will be considered both prior and concomitant if the start date of the medication is prior to the first dose of study medication and the end date is on or after the first dose of study medication.

If the start date and/or end date of a non-study medication is missing or partially missing, the noncomplete date should be compared to the first dose date of study medication whenever possible. Non-study medication will be considered as concomitant medication unless there is clear evidence that the start date of the non-study medication is earlier than the first dose date of study medication. If there is clear evidence that the start date of the non-study medication is earlier than the first dose date of study medication, the non-study medication will be considered both prior and concomitant unless there is clear evidence that the end date is earlier than the first dose date of study medication. If there is clear evidence that the end date of the non-study medication is earlier than the first dose date of study medication, then the non-study medication will be considered as prior medication.

Prior and concomitant medications will be summarized by Anatomic Therapeutic Chemical (ATC) Grade 4 and Preferred Term (PT) and listed in detail for subjects in the FAS.

Prior and concomitant surgeries/procedures

Prior surgeries/procedures include surgeries/procedures (that are not prior anti-cancer therapies) with both start and end dates prior to the first dose date of study drug. Concomitant surgeries/procedures included surgeries/procedures with start date on or after the first dose date of study medication and no later than 30 days after the last dose date of study medication. If the start date of a surgery/procedure is before the first dose date of study medication and the end date is on or after the first dose date of study medication, then it will be considered both prior and concomitant. If the start date and/or end date are missing or partially missing, the criteria for judging whether a surgery/procedure is prior or concomitant are the same as for prior and concomitant medications.

Prior and concomitant surgeries/procedures will be summarized by SOC and PT for subjects in the FAS and listed in detail.

8.3. Treatment Compliance and Exposure

Investigate the exposure of study treatment and calculate the duration and amount of exposure, as well as dose intensity, of the study treatment GFH018 for subjects in each dose group.

Duration of exposure

Duration of exposure (days) = last dose date - first dose date + 1

Actual dose intensity

Actual dose intensity (mg/day) = actual total cumulative dose (mg) / actual cumulative days with treatment administered (days)

Treatment compliance

Planned cumulative dose: total planned dose before the decision of treatment discontinuation.

Actual cumulative dose: total actual dose before the decision of treatment discontinuation.

Treatment compliance (%) = actual cumulative dose / planned cumulative dose \times 100%

Summarize actual total cumulative dose (mg), duration of exposure (days), actual dose intensity (mg/day), and treatment compliance (%) for subjects in the SS, and summarize treatment interruptions. Categorize treatment compliance by < 80%, 80% to 120%, and > 120%, and summarize the number and percentage of subjects under each category. List in detail subjects' first and last dose dates, duration of exposure, treatment adjustments, and reasons for the adjustments.

8.4. Safety Analysis

All safety analyses will be based on the safety set (SS), except for the DLT analysis which will be based on the dose-determining set (DDS). Baseline definition for safety analyses are provided in Section 8.1.

8.4.1. Adverse Events

Adverse events (AEs) will be coded using MedDRA version 25.0.

AE summary tables will include only TEAEs, while listings will include all AEs; AE incidence will be calculated based on the number of subjects with adverse events, and when a subject experiences multiple occurrences of the same AE under the same SOC and PT, the occurrence with the most severe grade will be counted. The following summaries and listings will be provided for AEs:

- Summarize the number and percentage of subjects with TEAEs, TEAEs with CTCAE Grade ≥ 3, treatment-related adverse events (TRAEs), TRAEs with CTCAE Grade ≥ 3, serious adverse events (SAEs), treatment-related serious adverse events (TRSAEs), AESI, DLT, TEAEs leading to treatment interruption, TRAEs leading to treatment interruption, TEAEs leading to dose reduction, TRAEs leading to treatment discontinuation, and TRAEs leading to treatment discontinuation.
- Summary of TEAEs by SOC, PT, and CTCAE Grade
- Summary of TRAEs by SOC, PT, and CTCAE Grade
- Summary of SAEs by SOC, PT, and CTCAE Grade
- Summary of TRSAEs by SOC, PT, and CTCAE Grade
- Summary of AESIs by SOC, PT, and CTCAE Grade
- Summary of TEAEs of Grade 3 or Higher by SOC, PT, and CTCAE Grade
- Summary of TRAEs of Grade 3 or Higher by SOC, PT, and CTCAE Grade
- Summary of DLTs by SOC, PT, and CTCAE Grade
- Summary of TEAEs leading to treatment interruption by SOC, PT, and CTCAE Grade
- Summary of TRAEs leading to treatment interruption by SOC, PT, and CTCAE Grade
- Summary of TEAEs leading to dose reduction by SOC, PT, and CTCAE Grade

- Summary of TRAEs leading to dose reduction by SOC, PT, and CTCAE Grade
- Summary of TEAEs leading to treatment discontinuation by SOC, PT, and CTCAE Grade
- Summary of TRAEs leading to treatment discontinuation by SOC, PT, and CTCAE Grade
- Summary of TEAEs by PT and CTCAE Grade, ordered in descending frequency
- Summary of TRAEs by PT and CTCAE Grade, ordered in descending frequency
- Summary of cause of death
- Listing of adverse events
- Listing of SAEs
- Listing of AESIs
- Listing of DLTs
- Listing of TEAEs leading to treatment interruption
- Listing of TEAEs leading to treatment discontinuation
- Listing of deaths

8.4.2. Laboratory Evaluations

By-visit descriptive summary will be provided for hematology, blood biochemistry, urinalysis (quantitative measurements), coagulation, thyroid function, and their changes from baseline.

For hematology, blood biochemistry, coagulation, and cardiac markers, changes in CTCAE grade from baseline (Grade 0 to 4, where Grade 0 is non-missing value other than Grade 1-4) to worst CTCAE grade after treatment starts (Grade 0 to 4, where Grade 0 means normal) will be summarized using shift tables. Test results from both scheduled and unscheduled visits will be included. For the tests without corresponding CTCAE grades, results in shift tables will be categorized into "lower than normal values and higher than normal values (i.e., both higher than normal values and lower than normal values occurred after first dose of treatment)", "lower than normal values", "normal values", and "higher than normal values". CTCAE grading reference ranges for laboratory tests are detailed in Appendix I.

Qualitative descriptive summaries will be provided for urinalysis (qualitative) results measured at each visit. A shift table will also be provided by normal, abnormal without clinical significance, and abnormal with clinical significance. For urine protein, a shift table by CTCAE grade will also be provided.

Laboratory test results will be listed separately for hematology, urinalysis, coagulation, blood biochemistry, virology, thyroid function, cardiac markers, and pregnancy test.

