4.1.2. Laboratory Tests

Please see Table 2 for the laboratory tests parameters.

Table 2 Laboratory tests parameters

Laboratory tests	Parameters
Hematology	Red blood cell count (RBC), hemoglobin concentration (HGB), hematocrit (HCT), mean red blood cell volume (MCV), mean red blood cell hemoglobin content (MCH), mean red blood cell hemoglobin concentration (MCHC), white blood cell count (WBC), platelet count (PLT), neutrophil count (ANC), lymphocyte (LY) count, monocytes (MO) count, eosinophil (EO) count, Basophil (BA) count, percentage neutrophils, percentage lymphocytes, percentage monocytes, percentage eosinophils, percentage basophils
Urinalysis	Urine leukocytes (LEU), urine nitrite (NIT), urine pH, urine specific gravity (SG), urine protein (PRO), urine glucose (GLU), urine ketone bodies (KET), urine bilinogen (UBG), urine bilirubin (BIL), urine occult blood (BLD), 24-hour protein*
Coagulation function	Prothrombin time (PT), activated partial thromboplastin time (APTT), international normalized ratio (INR)
Chemistry	Aspartate aminotransferase (AST), alanine aminotransferase (ALT), alkaline phosphatase (ALP), lactate dehydrogenase (LDH), glutamyl transpeptidase (GGT), urea (UREA)/urea nitrogen, blood creatinine (CREA), total protein (TP), albumin (ALB), white globular ratio (A/G ratio), total bilirubin (TBIL), direct bilirubin (DBIL), creatine kinase (CK), pancreatic amylase (AMY), fasting blood glucose (FPG), total cholesterol (TCHO), low-density lipoprotein cholesterol (LDL-C), high-density lipoprotein cholesterol (HDL-C), triglycerides (TG), bicarbonate, phosphate, calcium, sodium, chloride, potassium
Virus testing	Hepatitis B surface antigen (HBsAg), hepatitis C virus antibody (anti-HCV), HIV antibody, treponemal antibody
Thyroid function tests	Free triiodothyronine (FT3), free thyroxine (FT4), and thyroid-stimulating hormone (TSH).
Cardiac markers	Hypertroponin T (or Hypertroponin I), brain natriuretic peptide (BNP), hs-CRP, cysteine protease inhibitor (Cystatin C)
Pregnancy test	Serum β-HCG pregnancy test (blood pregnancy test in women of childbearing age)

^{*} For routine urinalysis, if the result of the fibrine test strip for urine protein is \geq 2+, a 24-hour urine sample should be collected for analysis.

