			3	$5.7 \text{ mmol/L} \leqslant \text{value} < 11.4 \text{ mmol/L or } 5.00 \text{ mg/dL} \leqslant \text{value} < 1000 \text{ mg/dL}$
			4	Value > 11.4 mmol/L or value > 1000 mg/dL
	Blood glucose	Decreased	1	$3. 0 \text{ mmol/L} \leq \text{value} < \text{LLN or } 5.5 \text{ mg/dL} \leq \text{value} < \text{LLN}$
			2	2 . 2 mmol/L \leq value \leq 3 . 0 mmol/L or 4 0 mg/dL \leq value \leq 5 5 mg/dL
			3	$\begin{array}{l} 1.7 \text{ mmol/L} \leqslant \text{value} < \\ 2.2 \text{ mmol/L or } 3.0 \\ \text{mg/dL} \leqslant \text{value} < 40 \\ \text{mg/dL} \end{array}$
			4	Value < 1 . 7 mmol/L or Value < 30 mg/dL
	Calcium	Increased	1	ULN < value ≤ 2.9 mmol/L or ULN < value ≤ 11.5 mg/dL
				2.9 mmol/L < value ≤ 3.1 mmol/L or 11.5 mg/dL < value ≤ 12.5
			2	mg/dL water = 12.5

Laboratory Test Category	Laboratory test indicators	Altered (increased/decreased)	CTCAE Grade	Criteria for judgment
			3	$3.1 \text{ mmol/L} < \text{value} \le 3.4 $ mmol/L or 12.5 mg/dL < $\text{value} \le 13.5 \text{ mg/dL}$
			4	Value > 3.4 mmol/L or Value > 13.5 mg/dL
		Decreased	1	$2.0 \text{ mmol/L} \leqslant \text{value} < \text{LLN or } 8.0 \text{ mg/dL} \leqslant \text{value} < \text{LLN}$
			2	$1.75 \text{ mmol/L} \leq \text{value} < 2.0 \text{ mmol/L or } 7.0 \text{ mg/dL} \leq \text{value} < 8.0 \text{ mg/dL}$
			3	$1.5 \text{ mmol/L} \le \text{value} < 1.75 \text{ mmol/L or } 6.0 \text{ mg/dL} \le \text{value} < 7.0 \text{ mg/dL}$
			4	Value < 1.5 mmol/L or Value < 6. 0 mg/dL
	Sodium	Increased	1	ULN < value ≤ 150 mmol/L
			2	150 mmol/L < value ≤ 155 mmol/L
			3	155 mmol/L < value ≤ 160 mmol/L
			4	Value > 160 mmol/L
		Decreased	1	$130 \text{ mmol/L} \leqslant \text{value} < \text{LLN}$
			3	$120 \text{ mmol/L} \leqslant \text{value} \leqslant 130 \text{ mmol/L}$
			4	Value < 120 mmol/L

Laboratory Test Category	Laboratory test indicators	Altered (increased/decreased)	CTCAE Grade	Criteria for judgment
	Potassium	Increased	1	ULN < value ≤ 5.5 mmol/L
			2	5.5 mmol/L < value ≤ 6.0 mmol/L
			3	6.0 mmol/L < value ≤ 7.0 mmol/L
			4	Value > 7.0 mmol/L
		Decreased	1	$3.0 \text{ mmol/L} \leqslant \text{value} < \text{LLN}$
			3	2.5 mmol/L ≤ value < 3.0 mmol/L
			4	Value < 2.5 mmol/L
Blood routine	Eosinophil (EO) count	Increased	1	Value > ULN and value > baseline
	Hemoglobin concentration (HGB)	Increased	1	$ ULN < value \le ULN + 2 $ g/d L
			2	$ULN + 20 g/L < value \le ULN + 40 g/L$
			3	Value > ULN + 40 g/L

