		Decreased	1	$100 \text{ g/L} \le \text{value} < \text{LLN}$ or $10 \cdot 0 \text{ g/dL} \le \text{value} < \text{LLN or } 6 \cdot 2 \text{ mmol/L} \le \text{value} < \text{LLN}$
			2	$8 \ 0 \ g/L \le value < 100$ $g/L \ or \ 8. \ 0 \ g/dL \le value$ $< 10 \ . \ 0 \ g/dL \ or \ 4.9$ $mmol/L \le value < 6.2$ mmol/L

Laboratory Test Category	Laboratory test indicators	Altered (increased/decreased)	CTCAE Grade	Criteria for judgment
			3	Value < 80 g/L or value < 8. 0 g/dL or value < 4.9 mmol/dL
	Lymphocyte (LY) count	Increased	2	$20,000/\text{mm}^{3} \le \text{value} < 4000/\text{mm}^{3} \text{ or } 20 - < 4 \text{ x} $ $10^{9}/\text{L}$
			3	Value > $20,000/\text{mm}^3$ or > $20 \times 10^9/\text{L}$
		Decreased	1	$800/\text{mm}^{3} \leq \text{value} < \text{LLN or} < \text{LLN - } 0.8 \times 10^{9}/\text{L}$
			2	$500/\text{mm}^{3} \le \text{value} < 800/\text{mm}^{3} \text{ or } < 0.8 - 0.5 \text{ x} $ $10^{9}/\text{L}$
			3	$200/\text{mm}^{3} \le \text{value} < 500/\text{mm}^{3} \text{ or } < 0.5 - 0.2 \text{ x} $ $10^{9}/\text{L}$
			4	Value < 200/mm ³ or < 0.2 x 10 ⁹ /L
	Neutrophil count (ANC)	Decreased	1	$1.5 \times 10^{9}/L \le \text{value} < \text{LLN or } 1500/\text{mm}^{3} \le \text{value} < \text{LLN}$
			2	1.0 x 10 9 /L \leq value $<$ 1.5 x 10 9 /L or 1 000/mm 3 \leq value $<$ 1 500/mm 3
			3	$0.5 \times 10^{9}/L \le \text{value} < 1.0 \times 10^{9}/L \text{ or } 500/\text{mm}^{3} \le \text{value} < 1000/\text{mm}^{3}$
			4	Value $< 0.5 \times 10^{9}/L$ or Value $< 5.00/mm^{3}$

				_
Laboratory Test Category	Laboratory test indicators	Altered (increased/decreased)	CTCAE Grade	Criteria for judgment
	Platelet count (PLT)	Decreased	1	75.0×10^{9} /L \leq value \leq LLN or 75000 /mm $^{3} \leq$ value \leq LLN
			2	$50.0 \times 10^{9}/L \le \text{value} < 75.0 \times 10^{9}/L \text{ or } 5 0000/\text{mm}^{3} \le \text{value} < 75000/\text{mm}^{3}$
			3	$25.0 \times 10^{9}/L \le \text{value} < 50.0 \times 10^{9}/L \text{ or } 2 $ $5000/\text{mm}^{3} \le \text{value} < 50000/\text{mm}^{3}$
			4	Value < 25.0 x 10 ⁹ /L or value < 2 5000/mm ³
	White blood cell count (WBC)	Decreased	1	$3.0 \times 10^{9}/L \le \text{value} < \text{LLN or } 3 000/\text{mm} ^3 \le \text{value} < \text{LLN}$
			2	$2.0 \times 10^{9}/L \le \text{value} < 3.0 \times 10^{9}/L \text{ or } 2000/\text{mm}$ $^{3} \le \text{value} < 3000/\text{mm}$
			3	$1.0 \times 10^{9}/L \le \text{value} < 2.0 \times 10^{9}/L \text{ or } 1000/\text{mm}$ $^{3} \le \text{value} < 2000/\text{mm}$

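### Blood glucose, white cells, neutrophils and platelets are graded only downwards, so the laboratory shift tables have no category for a high post-treatment value of these four tests

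*SAP*

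**What the plan says.** SAP section 8.4.2 specifies two kinds of laboratory shift table.

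- Hematology, biochemistry, coagulation and cardiac markers are tabulated by CTCAE grade, from baseline "to worst CTCAE grade after treatment starts (Grade 0 to 4, where Grade 0 means normal) will be summarized using shift tables". Results from scheduled and unscheduled visits both count.
- A low/normal/high table serves the remaining tests: "For the tests without corresponding CTCAE grades, results in shift tables will be categorized into" four classes, one of them for subjects in whom "both higher than normal values and lower than normal values occurred after first dose of treatment".

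Grade 0 has two definitions in the same sentence. At baseline, "Grade 0 is non-missing value other than Grade 1-4". After treatment starts, "Grade 0 means normal".

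Section 8.4.2 takes the grading limits from Appendix I. There the glucose entry reads "Blood glucose Decreased" and the white cell entry "White blood cell count (WBC) Decreased". ANC and platelets are likewise graded only as decreased. None of the four has an increased block. All four are collected under section 4.1.2, Table 2, where glucose is listed among the chemistry tests as "fasting blood glucose (FPG)".

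**The concern.** The rule that selects the format works per test, while the grades in Appendix I work per direction. A test graded in one direction only counts as a graded test, so it is kept out of the low/normal/high table, yet its grades say nothing about the other direction.

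For glucose, WBC, ANC and platelets the uncovered direction is the high one. A reader of the shift table who sees Grade 0 after treatment, with the SAP's own gloss on that label, would conclude that no abnormality occurred. Safety and tolerability are a primary objective (section 2) and escalation cohorts have 3 to 6 subjects (section 6), so one or two subjects with a clear rise would be a visible share of a cohort.

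**Working it through.** No sample size, power or error rate is involved. The check applies the rule of section 8.4.2 to the rows of Appendix I.

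**Step 1: directions graded in Appendix I, blood tests only.**

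| Directions graded | Tests | Count |
|---|---|---|
| Both | calcium, sodium, potassium, hemoglobin, lymphocytes | 5 |
| Decreased only | albumin, blood glucose, ANC, platelets, WBC | 5 |
| Increased only | AST, ALT, ALP, GGT, creatinine, total bilirubin, CK, total cholesterol, triglycerides, eosinophils, APTT, INR | 12 |

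Tests graded in one direction: 5 + 12 = 17. The entries for the four tests at issue are complete, each running from Grade 1 to Grade 4. Their missing high side is therefore not a gap in the extracted text.

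**Step 2: which table do the four tests enter?** They have grades, so they go to the CTCAE-grade table. The low/normal/high table is for tests without grades. Its combined low-and-high class shows that it was designed for whole tests, not for one remaining direction.

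**Step 3: where does a value above ULN go?** For each of the four tests, Grade 1 ends at the lower limit of normal and Grades 2 to 4 lie below Grade 1. A value above ULN therefore meets none of them.

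- *Baseline:* Grade 0, by the residual definition.
- *After treatment, no graded low value:* the only cell left is Grade 0, which is described as normal. Read strictly, a high value is not normal and so has no cell at all. Neither reading shows it.
- *After treatment, with a graded low value:* the subject appears at the worst low grade and the high value is hidden.

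**Step 4: illustration with assumed values.** Take a subject whose fasting glucose goes from 5.5 to 18 mmol/L, with an assumed ULN of about 6 mmol/L. No decreased criterion is met at either time, so the entry is Grade 0 to Grade 0. The result is the same for any ULN from 5.5 to just under 18 mmol/L. If two subjects in a cohort of six had such a course, the true share with a post-treatment high would be 2/6 = 33%, and the share visible in the shift table would be 0/6 = 0%. The SAP gives neither the ULN nor any expected rate of such rises.

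**Step 5: where does the high value still appear?**

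- By-visit summaries and changes from baseline (section 8.4.2), which under section 8.1 include the maximum. A maximum shows that an extreme occurred, not how many subjects moved from normal to high.
- Listings of laboratory results (section 8.4.2). No flag for abnormal values is specified there, whereas section 8.4.3 specifies one for vital signs.
- Adverse event tables (section 8.4.1), if the investigator reported the finding as an event.

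**The case against.** The strongest reply is that one descriptive display is affected. In a cohort of six, an extreme value at a summarised visit would be printed as the maximum, and every result is listed. Under section 3, escalation rests on the Safety Monitoring Committee's review of DLTs, other adverse events of grade 2 and above, and PK and pharmacodynamic data. Section 5 states that no hypothesis is tested, and no decision in the SAP is tied to a shift table. All of this stands, and it limits the point.

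A second reply is that Appendix I is laid out by direction, so a programmer might treat each direction as the graded unit and add a high-side table. That is possible, but section 8.4.2 speaks of tests, and the combined low-and-high class fits that wording. The output should not depend on a reading that the text does not give.

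A third reply is that if the residual definition of Grade 0 were used throughout, the table would be silent about high values, not wrong. This is fair. It removes the misleading label but leaves the high value without a category.

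A reader might also infer that every high value of these tests becomes Grade 0 and disappears from the safety report, or that the primary safety objective is compromised. The document supports neither. A subject with a graded low value is shown at that grade, the outputs in step 5 keep the high values, and no dose decision uses these tables. Nor is the 33% against 0% an estimate of impact: it rests on assumed values. The SAP does not name high glucose, leukocytosis or thrombocytosis as expected risks, and its adverse events of special interest are cardiac (section 4.1.1).

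**Conclusion.** The point holds as a defect of the shift tables for four tests. Followed as written, section 8.4.2 with Appendix I gives a post-treatment value above ULN for glucose, WBC, ANC or platelets no category other than a Grade 0 described as normal, or hides it behind a low grade.

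It matters because, among the laboratory summary tables, the shift table is the one specified by worst post-treatment result with unscheduled visits included. The by-visit summaries do not replace that view. It is more than a missing detail, because following the rule yields a misleading table. It remains a modest reporting matter, since the data stay visible elsewhere and no decision rule depends on the display.

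The conclusion rests on the plain wording of the SAP: format assigned per test, and grades as printed in Appendix I. It does not depend on what CTCAE v5.0 itself grades, which cannot be checked from this document. How many subjects would be affected cannot be derived from the SAP.

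**What to change.** Two changes to section 8.4.2.

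1. Use one definition of Grade 0 at baseline and after treatment: a non-missing value that does not meet Grade 1 to 4 in the graded direction. Drop the description of Grade 0 as normal.
2. State that for blood glucose, WBC, ANC and platelets, which Appendix I grades only as decreased, the existing low/normal/high shift table is provided in addition to the grade table. Add other one-direction tests only where the sponsor considers the ungraded direction relevant.

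A general rule covering every ungraded direction is not advised. It would reach all 17 one-direction tests, and many of the added tables, such as those for low ALT or low CK, would probably say little.

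The cost is a short change of wording and about four extra tables from data already collected, more if further tests are included. The display is already defined in the SAP, and nothing in the design, dosing or data collection changes.

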8.4.3. Vital Signs

By-visit descriptive summary will be provided for vital sign measurements (body temperature, heart rate, respiratory rate, systolic and diastolic blood pressure) and their changes from baseline. Changes from baseline to worst post-baseline measurements will be summarized in shift table according to the table below (Table 4). The number and percentage of subjects with significant changes in vital sign measurements will be summarized for each group.

Table 4 Criteria for Significant Changes in Vital Signs from Baseline

	Above Normal	Below Normal
Systolic Blood Pressure (mmHg)	increase $>$ = 20 from baseline, and $>$ = 160	Decrease $> = 20$ from baseline, and $< = 80$
Diastolic Blood Pressure (mmHg)	increase $>$ = 15 from baseline, and $>$ = 100	Decrease $> = 15$ from baseline, and $< = 50$
Heart Rate (beats/min)	increase $>$ = 15 from baseline, and $>$ = 100	Decrease $> = 15$ from baseline, and $< = 60$
Respiratory rate (breaths/min)	> 24	< 8
Body Temperature (°C)	>= 39.1	-

Vital signs for each subject will be listed in detail, and values with significant changes from baseline will be flagged.

8.4.4. 12-Lead Electrocardiogram

Descriptive summaries will be provided for each electrocardiogram (ECG) parameter measured at each visit and their corresponding changes from baseline (averaged over the three measurements).

According to Table 5, the number and percentage of subjects with abnormal changes in ECG parameters after treatment start will be summarized, and summaries will be provided in shift table for the worst change from baseline. ECG results for each subject will be listed in detail.

Table 5 Criteria for Significant Changes in ECG Indicators from Baseline

	Above Normal	Below Normal
QTcF (ms)	> 450 and $<$ = 480	-
	> 480 and $<$ = 500	-
	> = 501, or $>$ 60 increase from baseline	-
QT (ms)	> 450 and < = 480	-
	> 480 and $<$ = 500	-
	>= 501, or > 60 increase from baseline	-
Heart Rate (beats/min)	> 25% increase from baseline and value >= 100	> 25% decrease from baseline and value <= 50
PR (ms)	> 25% increase from baseline and value > 200	> 25% decrease from baseline and value < 120

	Above Normal	Below Normal
QRS (ms)	> 25% increase from baseline and value > 110	-

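### The vital-sign shift table in SAP Section 8.4.3 uses categories that no baseline blood pressure or heart rate can meet, so its abnormal baseline rows are empty by construction

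*SAP*

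**What the plan says.** SAP Section 8.4.3 plans by-visit summaries, a shift table, a count of subjects with significant changes, and a full listing in which significant changes are flagged. The shift table is defined this way: "Changes from baseline to worst post-baseline measurements will be summarized in shift table according to the table below (Table 4"). The table it refers to is headed "Table 4 Criteria for Significant Changes in Vital Signs from Baseline", and its two columns are labelled *Above Normal* and *Below Normal*.

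For systolic pressure the two entries are "increase $>$ = 20 from baseline, and $>$ = 160" and "Decrease $> = 20$ from baseline, and $< = 80". Diastolic pressure and heart rate follow the same pattern, with a change of at least 15 in each direction. Respiratory rate and body temperature carry absolute limits only. Table 4 has no category for values that fall in neither column, and the SAP gives no other range for classifying blood pressure or heart rate.

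Section 8.1 takes baseline as the last available measurement on or before the first dose.

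**The concern.** A shift table crosses the category a subject was in at baseline with the worst category reached afterwards. It therefore needs categories that can be assigned at both times. The blood pressure and heart rate rows of Table 4 describe an event (a change of a given size that ends past a limit), and an event of that kind cannot be assigned to the baseline value.

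Two things follow if the table is programmed as written. Subjects who entered with a high or low value are not identified, which is the main reason for choosing a shift table over a simple count. And a subject whose post-dose value lies past the limit, but whose change is just short, is placed in neither abnormal category. Safety and tolerability are primary objectives of this trial, so its safety tables should show what their titles promise.

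**Working it through.** The SAP states no figure on this point, so there is nothing to reproduce. The check applies the Table 4 rules exactly as written.

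**Inputs (Table 4, with the baseline definition from Section 8.1)**

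| Parameter | *Above Normal* | *Below Normal* |
|---|---|---|
| Systolic (mmHg) | rise ≥ 20 and value ≥ 160 | fall ≥ 20 and value ≤ 80 |
| Diastolic (mmHg) | rise ≥ 15 and value ≥ 100 | fall ≥ 15 and value ≤ 50 |
| Heart rate (beats/min) | rise ≥ 15 and value ≥ 100 | fall ≥ 15 and value ≤ 60 |

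**Step 1: the baseline margin.** For a baseline value B, the change is B − B = 0. Since 0 < 15 and 0 < 20, neither category can be met whatever B is. Classifying every whole-number baseline over wide ranges (systolic 60–220, diastolic 30–140, heart rate 30–180) put all of them in neither category. A subject at systolic 170 before dosing and 150 after is in neither category at both times and shows no shift.

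**Step 2: which baselines are exposed after dosing.** A value past the upper limit can escape classification when B > upper limit − required rise. A value past the lower limit can escape when B < lower limit + required fall.

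| Parameter | High values can escape when | Low values can escape when |
|---|---|---|
| Systolic | B > 160 − 20 = 140 | B < 80 + 20 = 100 |
| Diastolic | B > 100 − 15 = 85 | B < 50 + 15 = 65 |
| Heart rate | B > 100 − 15 = 85 | B < 60 + 15 = 75 |

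With whole-number readings, the largest change that escapes is 19 for systolic pressure and 14 for the other two.

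**Step 3: examples.**

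| Pair | Change | Past the limit? | Category under Table 4 |
|---|---|---|---|
| Systolic 95 → 76 | −19 | yes (≤ 80) | neither |
| Systolic 150 → 168 | +18 | yes (≥ 160) | neither |
| Diastolic 90 → 104 | +14 | yes (≥ 100) | neither |
| Heart rate 110 → 124 | +14 | yes (≥ 100) | neither |
| Systolic 140 → 160 | +20 | yes (≥ 160) | *Above Normal* |

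**Step 4: comparison within the SAP.** Other shift tables use states that fit both times: low, normal and high for laboratory tests without a CTCAE grade (Section 8.4.2), and three normal/abnormal states for physical examination (Section 8.4.5) and valve function (Section 8.4.7). The respiratory rate and temperature rows of Table 4 can also be assigned at baseline. The problem is specific to the three rows above.

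**The case against.** The best defence is that Table 4 is a list of significant-change criteria, as its title says. Requiring both a limit and a minimum change is a deliberate way to ignore small movements, and any threshold has cases just short of it. That stands for the count of significant changes and the listing flag, where the combined criteria are coherent for these three parameters. It does not rescue the shift table, which the same paragraph ties to the same criteria.

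Several stronger readings are tempting, and the SAP does not support them:

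- A reader might infer that the missed values are reported as normal. Table 4 names no normal category; that label is only suggested by the column headings. The SAP leaves the category unnamed.
- A reader might infer a threat to monitoring of the drug's cardiac risk or to escalation decisions. The adverse events of special interest in Section 4.1.1 are BNP or troponin elevation and abnormal cardiac ultrasound, and these have their own outputs. Section 3 describes the committee's review as resting mainly on dose-limiting toxicities, other adverse events of grade 2 and above, and pharmacokinetic and pharmacodynamic data. It does not mention this table.
- A reader might extend the fault to Table 5. Section 8.4.4 words its output differently: "summaries will be provided in shift table for the worst change from baseline". That can mean classifying the change alone, in which case no baseline row is needed. The QT and QTcF bands are largely absolute.
- A reader might see the opposite fault in the respiratory rate and temperature rows, because an unchanged 26 breaths/min meets a criterion titled as a change. That concerns the count and the flag, and does not make the shift table unworkable.

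It is also true that raw values survive in the by-visit summaries and full listings, and that events reported as adverse events are tabulated by grade. Values that just miss the change condition would, however, be unflagged in the listing.

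**Conclusion.** The point holds for systolic pressure, diastolic pressure and heart rate in the Section 8.4.3 shift table. As written, the rule gives a table with no abnormal baseline rows, whatever population is enrolled. It cannot show pre-existing abnormality, and it leaves some post-dose values past Table 4's own limits outside both abnormal categories.

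The size is modest. One descriptive safety table is affected; the SAP tests no hypothesis, and no primary result is shown to depend on this table. How many subjects would be affected cannot be estimated from the SAP. One subject in a cohort of 3–6 is 1/6 to 1/3 of it (17–33%), but that is true of any single subject and is not evidence of frequency.

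The conclusion assumes that shift table carries its usual meaning, a baseline category crossed with a worst post-baseline category, and that Table 4 supplies the categories for both.

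**What to change.** In Section 8.4.3, separate the two uses of Table 4:

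1. For the systolic, diastolic and heart rate shift tables, classify both the baseline and the worst post-baseline value by absolute limits alone. Table 4 already contains usable limits: systolic ≥ 160 / ≤ 80, diastolic ≥ 100 / ≤ 50, heart rate ≥ 100 / ≤ 60. The study team should confirm the heart rate cut-offs, because 60 and 100 were set for use together with a change condition.
2. Name the category for values within the limits.
3. Keep the combined limit-plus-change criteria for the count of subjects with significant changes and for the listing flag.
4. State whether the Section 8.4.4 table is a baseline-by-worst grid. If it is, check the heart rate, PR and QRS rows of Table 5, which combine a change above 25% with a limit, for the same problem.

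The cost is SAP wording and table shells; the same data are used. The downside is small: a few subjects with stable borderline values, such as a heart rate that stays at 58–60, will appear as abnormal at both times.
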